#### 19. If male,

EITHER be non-vasectomized and agrees to use a condom with spermicide or abstain from sexual intercourse during the study until 90 days after the last dose of study medication and the female partner agrees to inclusion criterion 18,

#### OR

be vasectomized at least 6 months prior to first dose and agrees to use a condom during sexual intercourse, or less than 6 months prior to first dose and must follow the same restrictions as a non-vasectomized male.

- 20. If treated with an AChEI, must be on a stable treatment for at least 12 weeks prior to the Baseline Visit and must be able to continue on the same drug for the duration of the study.
- 21. If treated with permitted antidepressants, mood stabilizers, or other psychotropic medications, must be on a stable dose according to [Table 1]. Only two anticonvulsants are permitted (for any use) as indicated in Table 1.
- 22. If taking permitted, non-psychotropic medications for the treatment of non-excluded medical conditions, must be on a stable dose according to [Table 1].

Confidential Page 43 of 115

#### **5.2.** Exclusion Criteria

To be considered eligible to participate in the study, the subject must not meet any of the following exclusion criteria:

- 1. Has a screening brain MRI indicative of significant abnormality per central reader, other than AD related atrophy, including, but not limited to,
  - prior large vascular territorial infarct,
  - > 2 lacunar infarcts (size > 1.5 cm) outside the brain stem,
  - severe white matter changes (deep white matter changes Fazekas grade = 3),
  - ventriculomegaly related to normal pressure hydrocephalus (after clinical correlation), or
  - aneurysm, subdural hematoma, abscess, or brain tumor (other than meningiomas or benign pituitary adenoma).

**Note 1**: A subject with any of the following conditions may be included in the study but requires prior approval from the Sponsor Medical Monitor:

- (a) > 10 microhemorrhages,
- (b) a focal area of superficial hemosiderosis > 1 cm,
- (c) prior hemorrhage > 1 cm^3
- (d) small vascular malformation, or
- (e) meningiomas  $\geq 1$  cm, or benign pituitary adenoma

**Note 2**: For a subject who cannot undergo MRI, brain CT is acceptable but requires prior approval from Medical Monitor. CT showing significant pathology per the central reader, other than AD related findings, will be excluded.

**Note 3**: CT is not allowed for subjects at sites in Germany.

- 2. Has a diagnosis of a neurodegenerative disorder other than AD.
- 3. Has been diagnosed with MDD according to the criteria of the Diagnostic and Statistical Manual of Mental Disorders Fifth Edition (DSM-5), within one year prior to the Baseline Visit. A subject who does not meet criteria for MDD and who is on stable doses of antidepressants or mood stabilizers may be included in the study at the discretion of the Investigator.
- 4. Is currently taking memantine or has taken memantine within 12 weeks prior to the Baseline Visit.
- 5. Has a history of suicidal behavior within one year prior to the Baseline Visit; or has ongoing suicidal ideation with intent, with or without a specific plan or method (e.g., positive response to C-SSRS items 4 or 5 during the past 6 months).
- 6. Has a history of seizures, excluding febrile seizures of childhood or a single distant seizure (> 5 years rior to the Baseline Visit).
- 7. Has a medically confirmed history of recent cerebral infarct or transient ischemic attack within one year prior to the Baseline Visit.
- 8. Has a medically confirmed history of recent myocardial infarction or unstable, untreated coronary artery disease, or angina pectoris within 1 year prior to the Baseline Visit.
- 9. Has a lifetime history of schizophrenia, schizoaffective disorder, or bipolar disorder.

Confidential Page 44 of 115

- 10. Has a history of, or currently has, any clinically significant ECG finding, or a QT interval corrected by Fridericia's method (QTcF) of > 450 msec for males and > 470 msec for females.
- 11. Has a history of cancer, diagnosed and treated within the last 3 years prior to the Baseline Visit, with the exception of the following: (a) treated basal cell carcinoma of the skin, (b) treated cutaneous squamous cell carcinoma in situ, (c) treated in situ or Stage 1 prostate cancer, (d) treated in situ cervical cancer, and (e) resected and cured early stage cutaneous melanoma (all require approval by the Sponsor's Medical Officer).
- 12. Has donated blood > 250 mL within 6 weeks prior to the Baseline Visit.
- 13. Has a history of alcohol or drug dependence or abuse according to the criteria of the DSM-5 within 2 years prior to the Baseline Visit.
  - **Note:** A positive urine drug screen does not automatically exclude the subject, but requires review by Sponsor Medical Officer.
- 14. Has any significant medical condition or infection (e.g., uncontrolled cardiovascular, GI, endocrinologic, hematologic, hepatic, immunologic, metabolic, urologic, pulmonary, neurologic, dermatologic, renal, or other major disease or malignancy) that is unstable and that would either: (a) place the subject at undue risk from administration of study drug or from undergoing study procedures, or (b) interfere with the interpretation of safety or efficacy evaluations obtained in the course of the study.
- 15. Is unable to swallow ALZ-801 tablets or has a known intolerance or hypersensitivity to tramiprosate or any of the excipients contained in the ALZ-801 tablets.
- 16. Except when otherwise specified, has clinical laboratory tests outside normal limits per the laboratory's specification and considered clinically significant by the investigator at the Screening Part 2 Visit.
- 17. Has clinically relevant abnormalities in serum thyroid-stimulating hormone (TSH) or calcium. If the subject is taking thyroid hormone replacement therapy, corresponding Screening test values must be considered not clinically significant by the investigator.
- 18. Has serum vitamin B12 below the lower limit of normal at the Screening Part 2 Visit. A subject can be rescreened if he/she receives vitamin B12 treatment, and has a normal vitamin B12 level at least four weeks post-treatment.
- 19. Has any clinical chemistry laboratory value greater than or equal to Common Terminology Criteria for Adverse Events (CTCAE; version 5.0; National Cancer Institute 2018) Grade 2, unless considered not clinically relevant by the Investigator.
- 20. Has one or more of the following at the Screening Part 2 Visit:
  - Alanine aminotransferase (ALT)  $> 3 \times$  upper limit of normal (ULN),
  - Aspartate aminotransferase (AST)  $> 3 \times ULN$ , or
  - Total bilirubin (TBL)  $> 1.5 \times \text{ULN}$  (except for subjects with diagnosed Gilbert syndrome with isolated hyperbilirubinemia).

Confidential Page 45 of 115

- 21. Has an estimated glomerular filtration rate (eGFR) < 40 mL/min per 1.73 m^2 according to the Modification of Diet in Renal Disease (MDRD) formula [see National Institute of Diabetes and Digestive and Kidney Diseases website for formula MDRD formula for eGFR (SI units)].
- 22. Has a glycosylated hemoglobin (HbA1c) > 8% (National Glycohemoglobin Standardization Program) or 64 mmol/mol (International Federation of Clinical Chemistry) at the Screening Part 2 Visit.
- 23. Only for subjects participating in the CSF sub-study: has impaired coagulation as determined by a prothrombin time (PT) according to the international normalized ratio (INR) > 1.5 or a platelet count  $< 50 \times 10^9$ /L prior to CSF sampling.
- 24. Has a history of human immunodeficiency virus (HIV), or hepatitis B or C, or positive serology at the Screening Part 2 Visit
  - **Note**: Subjects with a history of hepatitis C who have been treated and cured (no detectable HCV RNA) are allowed.
- 25. Has participated in a clinical trial of any investigational drug, device, or experimental medication or intervention within 24 weeks prior to the Baseline Visit [Table 1].
- 26. Has participated in a clinical study and received active treatment with an anti-amyloid vaccine or an anti-tau vaccine [Table 1].
- 27. Has received any of the treatments listed in [Table 1] more recently than the indicated period prior to the Baseline Visit or plans to receive any of those during the study.
- 28. Anticipates receiving any of the treatment listed in [Table 1] during the current clinical study, or is currently participating in an ongoing clinical trial or plans to participate in a future clinical trial during the conduct of this study.

# 5.3. Prohibited Medications and Exceptions

 Table 1
 Prohibited Medications and Specified Washout Period

Prohibited Medications and Exceptions	Washout Period Before Baseline Visit (Visit 2)		
Anti-amyloid or Anti-tau vaccine: Subjects who received active drug in a vaccine study are not eligible (subjects who received placebo are eligible)	Any use		

Confidential Page 46 of 115

Prohibited Medications and Exceptions	Washout Period Before Baseline Visit (Visit 2)		
Potential disease modifying AD treatment: Subjects who received aducanumab treatment (US subjects) or who participated in a clinical study and received active drug:	24 weeks		
Anti-amyloid or anti-tau antibodies (passive immunotherapy)			

 
β-secretase or β-site amyloid precursor protein cleaving enzyme (BACE) inhibitors
 
			
Amyloid anti-aggregation agents			
Anti-complement, anti-inflammatory, kinase inhibitors or other mechanisms			
AChEI: Subject should remain on the same drug at the same dose during the study.	Not applicable		
Exception: During the study, down titration to a lower dose is allowed if necessary because of tolerability issues. This dose adjustment requires			
discussion with the Sponsor Medical Monitor.			
Memantine: Memantine is not approved for subjects with MCI or Mild AD, and is not allowed in the study. Subjects requiring memantine after randomization must be withdrawn from the study.	12 weeks		
Anti-parkinsonian medications: For example, L-dopa, amantadine,	12 weeks		
bromocriptine, pergolide, selegiline, I-deprenyl/selegiline, rasagiline).			
[Subjects with Parkinson's disease are excluded from the study.]			
Exception: carbidopa/levodopa and dopamine agonists are allowed for			
treating restless leg syndrome, but dose should be stable for at least 4			
weeks prior to the Baselne Visit.			
Oral Anticholinergic medications: Regularly used (> 3 doses/week)	4 weeks		
anticholinergic medications of $\geq$ moderate potency (e.g., benztropine,			
cyclobenzaprine, cyproheptadine, dicyclomine, diphenhydramine,			
promethazine, diphenoxylate with atropine, hydroxyzine, hyoscyamine,			
prochlorperazine, trihexyphenidyl, trimethobenzamide).			
[These drugs may interfere with cognitive assessments.]	4 1		
Overactive Bladder medications: Oxybutynin.	4 weeks		
[The anticholinergic effect of this drug may interfere with cognitive			
assessments.] Exception: Daily use of the following medications are allowed:			
mirabegron, tolterodine, darifenacin, solifenacin, trospium, fesoterodine.			
Extended release formulations, where available, are preferred.			
Botulinum neurotoxin injection is allowed.			

Confidential Page 47 of 115

Prohibited Medications and Exceptions	Washout Period Before Baseline		
Antidonyaggants MAO inhibitans on antidonyaggants with a madanata	Visit (Visit 2) 4 weeks		
Antidepressants: MAO inhibitors or antidepressants with ≥ moderate	4 weeks		
anticholinergic potency, including tricyclic antidepressants.			
Examples of prohibited antidepressants are: amitryptyline, amoxapine,			
clomipramine, desipramine, imipramine, isocarboxazide, maprotiline,			
nortriptyline, phenelzine, protriptyline, tranylcypromine, trimipramine.			
Exception: Use of antidepressants with < moderate anticholinergic			
potency such as SSRIs or SNRIs are acceptable if stable for at least 4			
weeks before the Screening – Part 2 Visit			
Examples of allowed antidepressants are: citalopram, escitalopram,			
fluoxetine, paroxetine, sertraline, serotonin, duloxetine, venlafaxine,			
desvenlafaxine, trazodone, and mirtazapine.			
Neuroleptics: Neuroleptics with ≥ moderate anticholinergic potency	4 weeks		
such as chlorpromazine, fluphenazine, loxapine, perphenazine,			
thioridazine, thiothixene, trifluoperazine, clozapine.			
Exception: Low doses of oral atypical antipsychotics are allowed, this includes			
First generation drugs (olanzapine, quetiapine, risperidone,			
ziprasidone)			
• Second generation drugs (aripiprazole, asenapine, brexipiprazole,			
cariprazine, iloperidone, lurasidone and paliperidone)			
Mood stabilizers and anticonvulsants: Lithium, valproic acid,	4 weeks		
phenytoin, levetiracetam, and carbamazepine.			
[These drugs may affect cognitive outcomes.]			
Exception: Use of pregabalin and gabapentin for neuropathic pain, and			
a stable low doses of zonisamide (≤ 100 mg/day) for pain, migraine, or			
sleep is acceptable.			

Confidential Page 48 of 115

Prohibited Medications and Exceptions	Washout Period Before Baseline Visit (Visit 2)
Sedatives/benzodiazepines: Regularly used (> 3 doses/week)	4 weeks
sedatives/benzodiazepines (e.g., chlordiazepoxide, clonazepam,	
diazepam, meprobamate).	
[These drugs may interfere with cognitive assessments of clinical	
status.]	
Exception: Daily use of the following medications is acceptable if	
stable for at least 4 weeks before the Baseline Visit:	

 
Hypnotic drugs used for insomnia, for example, zaleplon ≤ 5 mg, zopiclone ≤ 7.5mg, eszopiclone ≤ 3mg, ramelteon ≤ 8 mg, suvorexant ≤ 15 mg, and zolpidem ≤ 5 mg (or equivalent doses of
 
	
same class)	
• Any as needed (prn) use $\leq 3$ days per week	
• Short term use with > 3 doses/week is acceptable, even if tested positive for sedatives/benzodiazepines, may enter the study. Short term use is defined as ≤ 1 month.	

 
Regular (> 3 days/week) use of low dose of
 
	
sedatives/benzodiazepines, for example, lorazepam, temazepam,	
flurazepam, triazolam, estazolam, and quazepam (or equivalent doses of same class) allowed if stable for at least 4 weeks before the Baseline Visit after review by Sponsor Medical Officer	

 
Regardless of sedatives/benzodiazepines usage, it is strongly recommended that subjects do not take these medications for at least 24 hours prior to cognitive assessments taken during clinic visits.
 
	
Analgesics/Narcotics: Regularly used (> 3 doses/week) narcotic	4 weeks
analgesics (e.g., codeine, morphine, hydromorphone, oxycodone, propoxyphene and its variations, & combination products that contain a narcotic).	
[These drugs may interfere with cognitive assessments of clinical	
status.]	
Exception: Short term use (< 1 month) more than 3 doses/week is	
acceptable for temporary conditions. Narcotics are not to be used within	
48 hours of cognitive testing at study visits.	
Stimulant medications: For example, amphetamine, methylphenidate,	4 weeks
atomoxetine, modafinil	
[These drugs may affect cognitive outcomes.]	

Confidential Page 49 of 115

Prohibited Medications and Exceptions	Washout Period Before Baseline Visit (Visit 2)
Anticoagulants: For example, warfarin, dabigatran, apixaban or other	4 weeks
blood factor or thrombin inhibitor.	
[Increased risk of cerebrovascular events in APOE4/4 homozygotes	
carriers with potential cerebral amyloid angiopathy; anticoagulants also	
increase potential risks associated with LP.]	
Exception: Use of single anti-platelet therapy (e.g., aspirin or	
dipyridamole or clopidogrel) is permitted. Use of dual anti-platelet	
therapy (low-dose aspirin with dipyridamole or clopidogrel) is	
permitted. Subjects on dual anti-platelet therapy may be allowed to	
participate in the CSF sub-study after discussion with Sponsor Medical	
Monitor.	
Corticosteroids: Systemic use: oral, intravenous, or intramuscular	4 weeks
[These drugs may affect assessment of the neuroinflammatory	
biomarkers.]	
Exceptions: The following are acceptable:	
• Low dose oral treatment with the equivalent of $\leq 10$ mg prednisone	
• Short-term oral treatment with the equivalent of ≤ 60mg	
prednisone for < 4 weeks	
• Local injections into joints or bursae; topical, inhaled, or nasal use	

BACE:  $\beta$ -secretase or  $\beta$ -site amyloid precursor protein cleaving enzyme; LP: lumbar puncture; MAO: monoamine oxidase; SNRI: serotonin and norepinephrine (noradrenaline) re-uptake inhibitors; SSRI: selective serotonin reuptake inhibitors.

**Note:** This is not a complete list of prohibited medications. Contact the Medical Monitor if there is a question about a specific medication.

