# 5.5. Subject Withdrawal, Termination, and Replacement

Study subjects may discontinue from the study or be withdrawn from the study for any of the following reasons:

- At the subject's or the subject's legally authorized representative with the subject's assent request for any reason (withdrawal of consent)
- Subject whose cognitive function declines and is deemed by the Investigator to be unable to provide assent/consent for continuation in the study
- At the discretion of the Investigator, if deemed appropriate, for any reason
- At the discretion of the Sponsor, if deemed appropriate, for any reason
- Subject for whom investigator deems initiation of memantine medically necessary must be withdrawn
- Subject noncompliance: If a subject takes less than 70% of study drug tablets, this may be considered reason for withdrawal, by Investigator or Sponsor request
- Protocol violation that compromises subject safety
- For safety concerns; medically significant AE(s) or SAE(s) with CTCAE > Grade 3 may be considered reason for withdrawal, if appropriate in the judgment of the Investigator
- Subject who becomes pregnant must be withdrawn from the study
- The subject's caregiver/study partner is no longer willing or able to participate in the study and a suitable replacement caregiver/study partner cannot be found
- Brain MRI findings: subject who has any of the following findings on central reading:
  - o Macrohemorrhage: defined as hemorrhage with size > 1 cm^3
  - o ARIA-E (vasogenic edema) associated with neurologic symptoms: dosing will be halted for 1 month and MRI repeated. Resumption of dosing may be considered after discussion between Investigator and Sponsor's medical officer.
- Subject who experiences an event of syncope without a clear triggering event (e.g., blood draw or pain inducing a vasovagal episode) will be withdrawn from the study
- Subject with clinically notable ECG abnormalities based on the average of triplicate ECG readings. The criteria for clinically notable or significant ECG results that require subject withdrawal are as follows:
  - o QTcF (Fridericia's correction) interval > 500 msec, and
  - An increase in QTcF interval of > 60 msec from baseline.

Confidential Page 51 of 115

**Note:** The criteria for QTcF are based on the upper threshold in elderly subjects who are known to have higher ULN [Reardon & Malik, 1996], and is the threshold commonly used in AD studies.

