## **Early Termination**

Should a study subject request or decide to withdraw or is withdrawn by Investigator or Sponsor, an Early Termination (ET) Visit will be conducted at the time of discontinuation. All efforts should be made to conduct assessments and to complete and report observations as thoroughly as possible up to the date of withdrawal, including all the evaluations shown in the Schedule of Assessments [Appendix 2]. All information will be reported on the applicable pages of the eCRF.

If the subject withdraws from the study due to an AE, every reasonable attempt should be made to follow the subject until the AE resolves or until the Investigator, after discussion with the Sponsor, deems the AE to be chronic or stable. All SAEs will continue to be followed for 4 weeks after the ET visit or until the AE is deemed to be either chronic or stable.

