#### 7.2.15. Retrieved Dropout Visit

In addition to the ET visit, subjects who discontinue the study drug during the trial will be encouraged to remain in the study (off study drug) for continued RDO visits by attending Week 52 (if applicable) and Week 78 (EOT) visits. The RDO visits will include the following procedures, in the recommended order shown below:

- Vital signs
- AE assessment
- Change in medications since last visit
- ADAS-Cog
- A-IADL
- MMSE
- NPI

For subjects who prematurely withdraw from the study,, they will be encouraged to return at Week 78 to finish study-related procedures.

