- Any study subject who becomes pregnant during the study must be withdrawn from treatment and will be followed to term and/or other pregnancy outcome.
- For all female study subjects, a serum pregnancy test must be performed at the Screening Part 2 Visit.

Confidential Page 81 of 115

- Females of non-childbearing potential are defined as follows:
  - o Be postmenopausal with amenorrhea for at least 1 year prior to the first dose and FSH serum levels consistent with postmenopausal status, or
  - O Have undergone one of the following documented sterilization procedures at least 6 months prior to the first dose:
    - hysteroscopic sterilization,
    - bilateral tubal ligation or bilateral salpingectomy,
    - hysterectomy, or
    - bilateral oophorectomy.
- Females of childbearing potential, defined as a premenopausal female capable of becoming pregnant, will be included if they are either sexually inactive (sexually abstinent for 14 days prior to the first dose and confirm to continue through 28 days after the last dose) or using one of the following highly effective contraceptives (i.e., results in < 1% failure rate when used consistently and correctly) 14 days prior to the first dose continuing through 28 days after the last dose:
  - o IUD,
  - o surgical sterilization of the partner (vasectomy for 6 months minimum),
  - o combined (estrogen or progestogen containing) hormonal contraception associated with the inhibition of ovulation (either oral, intravaginal, or transdermal),
  - o progestogen only hormonal contraception associated with the inhibition of ovulation (either oral, injectable, or implantable),
  - o IUS, or
  - o bilateral tubal occlusion.

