#### 10.7.2. Primary Efficacy Analysis

Unless otherwise specified, all primary efficacy analyses will be performed using the mITT population. Analyses of the primary endpoint of ADAS-Cog 13 will be performed with a likelihood based linear MMRM on treatment observed case (OC) data. The OC data set will consist of actual observations recorded at each visit during the double-blind treatment period and no missing data will be imputed. The model terms will include treatment, the stratification factors of use of concomitant AD medications (AChEI or none), age group (50 through 65 years or > 65 at the Screening – Part 1 Visit), gender, disease severity based on MMSE at the Baseline Visit, baseline ADAS-Cog 13 values, visit (VISIT), and treatment by visit interaction. The visit variable will be used to define the within-subject repeated measures over time. The least squares mean (LSM) for each treatment at each visit will be generated together with its 95% confidence interval, and the LSM difference between the active treatment and placebo will also be calculated; together

Confidential Page 94 of 115

with its standard error, and the 2-sided 95% confidence interval. For the primary endpoint at 78 weeks, treatment comparisons will be done at the 0.05 significance level.

All data collected during the study will be used in the statistical analysis. Additional details will be described in the final SAP. Sensitivity testing of the primary endpoint will include MMRM analyses for the PPP, and the CP.

For subjects who discontinue treatment prior to trial completion, every attempt will be made to have them continue with clinic visits and study assessments. Particular attention will be given to collecting Week 78 ADAS-Cog 13 assessments, regardless of when subjects discontinued treatment. These data from retrieved dropouts data will be used to impute missing data using multiple imputation method as a sensitivity analysis for the primary endpoint. This method assumes that the best reflection of what happened to the early dropout patients at Week 78 are the retrieved dropouts. For those subjects who terminate treatment prematurely but have Week 78 assessments, and the intermediate missing off-treatment data will be imputed by interpolation for analyses.

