7 STUDY SUBJECTS

7.1 Subject Disposition

The number of subjects screened and randomized will be provided. For subjects who were screened but not randomized (screen failures), the counts and reasons for screen failures will be summarized. The number of subjects who withdrew from the study before Week 78 will also be provided (Early Terminations, ET) and the reasons for ET will be provided as listing

and summarized in Tables. The subset of ET subjects who discontinued study drug but attended study visits and provided further assessments (retrieved dropouts [RDOs]) will also be provided as listing and summarized in Tables. The number of subjects whose study drug was suspended by the Sponsor or investigator, and reason for study drug suspension will also be summarized.

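### The rule that withdraws memantine starters from the study works against the SAP's treatment-policy primary analysis, which needs their later ADAS-Cog 13 scores

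*Protocol*

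**What the plan says.** **The rule.** Protocol Table 1 (Section 5.3): "Subjects requiring memantine after randomization must be withdrawn from the study". Protocol Section 5.5, in a list of reasons for leaving the study: "Subject for whom investigator deems initiation of memantine medically necessary must be withdrawn".

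**The analysis.** SAP Table 16 and the text of Section 8.3.1 adopt a treatment-policy strategy for the primary endpoint. Scores after treatment discontinuation, withdrawal or symptomatic AD medication are used, not treated as missing. SAP Section 8.3.2 defines those medications as AChE inhibitors or memantine.

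**The follow-up intent.** Protocol Section 10.7.2: "For subjects who discontinue treatment prior to trial completion, every attempt will be made to have them continue with clinic visits and study assessments". It puts special emphasis on the Week 78 ADAS-Cog 13, whenever treatment stopped. SAP Section 8.3.1 repeats this.

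**What a withdrawn subject is offered.** Under Section 5.5, "an Early Termination (ET) Visit will be conducted at the time of discontinuation". Section 7.2.15 then has two routes. Subjects who stop study drug but stay in the study are encouraged to attend retrieved-dropout visits at Week 52 (if applicable) and Week 78. For those who leave the study early, "they will be encouraged to return at Week 78 to finish study-related procedures". The Synopsis words that second route for subjects who choose to withdraw. Neither text mentions subjects withdrawn under the memantine rule.

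**The concern.** Memantine use is an intercurrent event whose later scores the primary estimand calls for, yet the rule for that event, as worded, takes the subject out of the study. Subjects judged to need memantine are likely to be among the faster decliners. If their Week 78 scores are absent, the MMRM predicts them from earlier scores under missing at random, and any decline beyond that prediction is lost. If more placebo than active subjects start memantine, the placebo arm then looks better than it should and the drug effect is understated.

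The planned safeguards are thin. SAP Section 8.3.2 says that missing-not-at-random methods will be considered but commits to none. The imputation from retrieved dropouts in Protocol Section 10.7.2 does not appear in the SAP. What is at stake is mainly whether the estimate matches the stated estimand.

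**Working it through.** **1. The plan's own power.** Inputs from Protocol Section 10.3.1 and SAP Section 4.1: SD 8.1 (drug) and 5.6 (placebo), 125 completers per arm, two-sided 0.05.

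- SE = sqrt((8.1² + 5.6²)/125) = sqrt(96.97/125) = 0.881.
- Normal-approximation power for 3.0 points: Φ(3.0/0.881 − 1.96) = 92.6%. The SAP says above 90%, the Protocol about 90%.
- For 2.5 points: 81.0%. The SAP says about 80%.

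**2. When an early-termination score helps.** SAP Table 5 assigns ADAS-Cog scores by study day: Week 52 is days 275–456 and Week 78 is days 457–592. Assume that memantine starts are uniform over days 2–547 (546 days).

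- Starts from day 457: 91/546 = 16.7%. The termination score fills Week 78.
- Starts before day 457: 455/546 = 83.3%. Week 78 needs a return visit.
- Starts before day 275: 273/546 = 50%. Only these can lack a Week 52 score, because later starters have a termination score or the regular visit in that window.

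A termination score may pre-date memantine, since withdrawal is triggered when the drug is judged necessary.

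**3. Illustrative shift.** The documents give no start rate, arm difference or excess decline. All of these are assumptions: 4% to 10% of placebo and half as many active subjects start (a difference of 0.02 to 0.05); true Week 78 scores are 3 to 9 points worse than the MMRM predicts; half of those who need a return visit return.

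Shift = excess decline × difference in start rates × share without a Week 78 score. Share missing = 0.833 × 0.5 = 0.4167.

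- Low: 3 × 0.02 × 0.4167 = 0.025 points.
- At 6 points, the planned placebo decline: 6 × 0.05 × 0.4167 = 0.125.
- High: 9 × 0.05 × 0.4167 = 0.1875, and 0.1875/0.881 = 0.21 SE.

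**4. Power if that shift stayed in the estimate.**

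| Per arm | True effect | No shift | Shift 0.025 | Shift 0.125 | Shift 0.1875 |
|---|---|---|---|---|---|
| 125 | 3.0 | 92.6% | 92.2% | 90.4% | 89.1% |
| 125 | 2.5 | 81.0% | 80.2% | 76.9% | 74.7% |
| 135 | 3.0 | 94.3% | – | – | 91.3% |
| 135 | 2.5 | 83.9% | – | – | 77.9% |

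The 135 rows use the 325 actually randomized: 325 × 0.83 / 2 = 134.9, SE 0.848.

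**5. What the fix could recover.** Step 4 compares no extra capture with complete capture. Retrieved-dropout visits are themselves only encouraged, so complete capture is an upper bound.

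- If return rises from 50% to 75%, the share recovered is 0.833 × 0.25 = 0.2083. The recovered shift is 3 × 0.02 × 0.2083 = 0.0125 to 9 × 0.05 × 0.2083 = 0.094 points. In the extreme case power for 3.0 points moves from 89.1% to about 91.0%.
- If return does not change, the fix recovers nothing.
- If start rates are equal by arm, the difference term is zero, so there is no shift to recover.

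**The case against.** The strongest reply is that withdrawal here does not end collection of the primary endpoint. SAP Section 8.3.1 lists withdrawal itself among the intercurrent events whose later scores are kept. SAP Section 7.1 counts retrieved dropouts as a subset of early terminations. Section 7.2.15 uses the same word, encouraged, for both routes to Week 78. Section 5.5 is also loose. It lists symptomatic ARIA-E, where dosing may resume, and pregnancy, although Section 8.1.2 says that a pregnant subject "must be withdrawn from treatment and will be followed to term and/or other pregnancy outcome". The rule also fits the Protocol's own on-treatment observed-case analysis (Section 10.7.2), and SAP Section 8.3.2 has a while-on-treatment supportive analysis.

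Most of this stands, and it makes the clash partial. It does not remove it. Table 1 says study, not treatment; nothing clarifies that for memantine; and the Week 52 visit is offered only to those who remain. The on-treatment wording explains where the rule came from, but the SAP now declares treatment policy. SAP Section 8.3.1 still describes on-treatment observed cases too, which is a separate inconsistency.

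The objection to the inputs also stands. Doubling the placebo start rate is a choice that forces a non-zero shift. The top case has an average start rate of (10% + 5%)/2 = 7.5%, which is 7.5/17 = 44% of all planned dropout, from a drug that Table 1 says is not approved for MCI or Mild AD.

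A reader might infer that the rule deprives the trial of these subjects' Week 78 data, or that it costs a known amount of power. The documents support neither: return at Week 78 is encouraged, and no start rate is given.

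**Conclusion.** The mismatch is in the text and worth correcting, as a cheap improvement in alignment with the estimand. It is not a demonstrated loss of power. The gain cannot be derived from the documents. The figure of about 0.19 points rests on the extreme assumptions in step 3 and on full Week 78 capture, so it bounds the gain under those assumptions and is not an expected value. The likely direction, more placebo than active starters, is conservative for the efficacy claim. That direction is itself an assumption; more active starters would reverse it. The point concerns memantine only.

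**What to change.** 1. Reword Protocol Table 1 and Section 5.5 so that subjects who need memantine stop study drug but remain in follow-up. State in Section 7.2.15 that the retrieved-dropout visits at Week 52 (if applicable) and Week 78 apply to them.
2. Add one SAP table by arm: memantine starters with and without a Week 78 ADAS-Cog 13 score, and how many of those scores are early-termination scores placed in the Week 78 window. SAP Sections 7.1 and 7.5 already summarize termination reasons, retrieved dropouts and concomitant medications, but do not cross them with each other or with Week 78 availability.

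**Cost.** A wording change, a few extra visits of a type already defined, and one table that needs no new data.

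**Limits.** Enrolment is complete at 325 (SAP Section 4.1) and the Protocol Synopsis expects the last subject to finish in August 2024, so the rewording helps only subjects who have not yet passed Week 78. The table is useful regardless. The retrieved-dropout visit list has ADAS-Cog, A-IADL, MMSE and NPI but no CDR, so no CDR-SB data are gained.
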